5.3.2 Secondary Efficacy Endpoint Analyses and Exploratory Endpoint Analyses

The secondary efficacy endpoints (percent change from baseline to Month 1 in LDL-C; change from baseline to Months 1 and 2 in LDL-C; percent change from baseline to Months 1 and 2 in ApoB, non-HDL-C, TC, and hs-CRP) will be analyzed using the ANCOVA method similar to the primary endpoint. Each ANCOVA will be performed using the mITT, with patients included in their randomized treatment group regardless of the treatment they actually received. Missing values will be imputed using LOCF, where

Confidential

Page 14 of 25

applicable. For each parameter and analysis time point, the LSM and SE will be provided for both treatment groups, along with the placebo-corrected LSM, its 95% CI and associated p value.

All efficacy endpoints will be analyzed at a significance level of 0.05, no multiplicity adjustment will be implemented. We will analyze observed data and LOCF data separately.

The same analysis will be performed as sensitivity analysis on treatment completer set for secondary efficacy endpoints.

The mean (\pm SE) will be plotted for secondary efficacy endpoints by visit.

Exploratory endpoints [REDACTED] will be summarized by descriptive statistics.

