### 13.5. Primary Endpoint

The primary efficacy endpoint is the percent change from baseline to Month 2 in LDL-C. The primary efficacy endpoint will be analyzed using analysis of covariance (ANCOVA), with

treatment group as a factor and baseline LDL-C as a covariate. The details of the ANCOVA model and options to correct for unequal variances will be described in the SAP. Baseline LDL-C is defined as the average of S4 and Day 1 values, if only 1 value is available, then that single value will be used as baseline. The ANCOVA will be performed using the FAS, with patients included in their randomized treatment group regardless of the treatment they actually received. Patients who are missing their Month 2 LDL-C will have their Month 2 value imputed by last observation carried forward (LOCF). The least squares mean (LSM) and standard error (SE) for percent change estimate will be provided for both treatment groups, along with the placebo-corrected LSM, its 95% confidence interval (CI) and associated p-value.

The ANCOVA assumptions will be examined and nonparametric test or transformation of the data will be considered if these assumptions are not met.

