### **13.6. Secondary and Exploratory Efficacy Endpoints**

The secondary efficacy endpoints (percent change from baseline to Month 1 in LDL-C; change from baseline to Months 1 and 2 in LDL-C; percent change from baseline to Months 1 and 2 in ApoB, non-HDL-C, TC, hs-CRP [REDACTED] and [REDACTED]), will be analyzed using the ANCOVA method similar to the primary endpoint. Baseline value for TC, non-HDL-C, [REDACTED] will be the average of S4 and Day 1 values; ApoB and hs-CRP will be the Day 1 value, if only 1 value is available, the single value will be used as the baseline. Each ANCOVA will be performed using the FAS, with patients included in their randomized treatment group regardless of the treatment they actually received. Missing values will be imputed using LOCF, where applicable. For each parameter and analysis time point, the LSM and SE will be provided for both treatment groups, along with the placebo-corrected LSM, its 95% CI and associated p value.

All efficacy endpoints will be analyzed at a significance level of 0.05, no multiplicity adjustment will be implemented.

Exploratory endpoints will be summarized by descriptive statistics.

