3.1 Objectives

The primary objective for this study is to assess the 2-month efficacy of bempedoic acid 180 mg/day versus placebo in the reduction of low-density lipoprotein cholesterol (LDL-C) in patients on proprotein convertase subtilisin/kexin type 9 inhibitor (PCSK9i) therapy.

The secondary objectives are:

- To assess the 1-month efficacy of bempedoic acid 180 mg/day versus placebo in the reduction of LDL-C in patients on PCSK9i therapy
- To evaluate the effect of bempedoic acid 180 mg/day versus placebo on apolipoprotein B (ApoB), non-high-density lipoprotein cholesterol (non-HDL-C), total cholesterol (TC), and high-sensitivity C-reactive protein (hs-CRP) after 1 and 2 months in patients on PCSK9i therapy
- To evaluate the safety and tolerability of bempedoic acid 180 mg/day compared to placebo in patients on PCSK9i therapy

The exploratory objectives are:

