5.3 Efficacy Endpoints and Analyses

5.3.1 For all efficacy endpoints and analyses, the Modified Intent to Treat (mITT) analysis set will be used. Primary Endpoint Analysis

The primary efficacy endpoint is the percent change from baseline to Month 2 in LDL-C. If triglycerides (TG) > 400 mg/dL or LDL-C < 50 mg/dL, LDL-M instead of LDL-C will be used as primary efficacy endpoint. The primary efficacy endpoint will be analyzed using analysis of covariance (ANCOVA), with treatment group as a factor and baseline LDL-C as a covariate. The ANCOVA will be performed using the mITT, with patients included in their randomized treatment group regardless of the treatment they actually received. Patients who are missing their Month 2 LDL-C will have their Month 2 value imputed by last post-baseline observation carried forward (LOCF). The least squares mean (LSM) and standard error (SE) for percent change estimate will be provided for both treatment groups, along with the placebo-corrected LSM, its 95% confidence interval (CI) and associated p-value.

The ANCOVA assumptions will be examined and nonparametric test or transformation of the data will be considered if these assumptions are not met. A non-parametric approach using Wilcoxon rank sum test will be performed on percent change from baseline for hs-CRP and TG. The median treatment difference (location shift) and 95% CI from Hodges-Lehmann estimates will be also presented.

An example sas code for ANCOVA analysis is shown as below:

```
PROC MIXED DATA=adxx method=reml;  
  class usubjid armcd;  
  model pchg = blres armcd / solution ddfm=kenwardroger;  
  repeated/group=armcd;  
  lsmeans armcd / diff cl;
```

Missing data for the primary endpoint will be imputed using the last post-baseline observation carried forward (LOCF) procedure (only post-baseline values will be carried forward).

A secondary analysis for the primary endpoint will be conducted use observed data only.

The same analysis will be performed as sensitivity analysis on treatment completer set for primary efficacy endpoint.

The mean (\pm SE) will be plotted for primary efficacy endpoint by visit.

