5.4.5 Vital Signs

Actual values and changes from baseline in vital signs (heart rate, systolic blood pressure, diastolic blood pressure, weight, height [baseline only], and BMI) will be summarized using descriptive statistics by treatment group and post-baseline time point on the observed values. Baseline is defined as the last value prior to the first dose of study medication.

Vital signs data will be listed for each patient, with increases from baseline of $> 15 \text{ mmHg}$ in systolic or diastolic blood pressure flagged.

For vital signs, observed values and changes from baseline will be summarized for all post-baseline study visits.

6 Changes in Statistical Analysis Plan Based on the Study-Specific Protocol

1. To be consistent with other Esperion studies, the LDL-M will be used as primary endpoint where triglycerides (TG) > 400 mg/dL or LDL-C < 50 mg/dL for primary efficacy endpoint analysis.
2. The treatment completer set will be used for sensitivity analyses of primary and secondary efficacy endpoints.
3. AEs during run-in period will be summarized.

7 Reference

2. World Health Organization (WHO) Fact Sheet No 317 Updated January 2015.

8 Appendices

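### Does hs-CRP need a single named main analysis, given that SAP 5.3.2 assigns it to ANCOVA and SAP 5.3.1 to the Wilcoxon test?

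*SAP*

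**What the plan says.** SAP 3.1 makes hs-CRP one of four parameters in a secondary objective, after ApoB, non-HDL-C and "total cholesterol (TC), and high-sensitivity C-reactive protein (hs-CRP) after 1 and 2 months in patients on PCSK9i therapy".

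SAP 5.3.2 ends its list of secondary efficacy endpoints with percent change at Months 1 and 2 "in ApoB, non-HDL-C, TC, and hs-CRP) will be analyzed using the ANCOVA method similar to the primary endpoint". It then sets the output without an exception for hs-CRP: "For each parameter and analysis time point, the LSM and SE will be provided for both treatment groups", together with the placebo-corrected LSM, its confidence interval and a p-value. Protocol 13.6 also lists hs-CRP among endpoints that "will be analyzed using the ANCOVA method similar to the primary endpoint".

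SAP 5.3.1, the section on the primary LDL-C endpoint, repeats a rule from protocol 13.5: "The ANCOVA assumptions will be examined and nonparametric test or transformation of the data will be considered if these assumptions are not met". The next sentence in the same paragraph is "A non-parametric approach using Wilcoxon rank sum test will be performed on percent change from baseline for hs-CRP and TG", followed by "The median treatment difference (location shift) and 95% CI from Hodges-Lehmann estimates will be also presented".

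SAP Section 6 lists three changes from the protocol. The hs-CRP method is not one of them.

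**The concern.** The same endpoint carries two firm assignments, in adjacent sections that do not refer to each other on this point. Neither analysis is called main, supportive or sensitivity, although the SAP does label other duplicates. Section 6, for instance, says "The treatment completer set will be used for sensitivity analyses of primary and secondary efficacy endpoints".

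Other text in the plan does not settle the matter. The rule that the SAP overrides the protocol does not reach a conflict inside the SAP. The word also in the Hodges-Lehmann sentence could mean beside the Wilcoxon p-value or beside the LSM.

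Read literally, hs-CRP gets two p-values and two effect measures per visit. A placebo-corrected LSM is a difference in mean percent change; a Hodges-Lehmann estimate is a location shift. On skewed data these can differ widely, and someone could lead with the more favourable one after seeing the results.

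**Working it through.** **1. Can both instructions be carried out?** Yes. Each specifies a test, an estimate and an interval on the same variable, and neither forbids the other. This is duplication without a ranking, not an impossibility.

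**2. Is there a natural reading?** SAP 5.3.2 defines its method by reference to the primary endpoint, which sends the reader to 5.3.1. There the fallback for failed assumptions is followed at once by a sentence naming hs-CRP and TG. That sentence has no function for LDL-C, so it most plausibly applies the fallback to the two parameters singled out. A sentence about two named parameters ordinarily qualifies a general list. On this reading Wilcoxon with Hodges-Lehmann leads and ANCOVA is shown beside it. The reading is inferred, not written.

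**3. How much could the missing label matter?** The plan gives no hs-CRP distribution or power figure, so there is nothing to reproduce. Only 26 per arm and the 0.05 level come from the documents. The rest is assumed: log-normal hs-CRP, log SD σ of 0.8 to 1.2, baseline to follow-up correlation ρ of 0.5 to 0.8, and true ratio of active to placebo of 1.0, 0.80 or 0.65. The simulation used 20,000 trials per cell (6,000 for Hodges-Lehmann) and ANCOVA with arm-specific variances, as in the SAP code.

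*No true effect.* ANCOVA rejects in 3.5-4.9% of trials, Wilcoxon in 4.7-5.1%, at least one in 6.8-7.3%. The identity is P(either) = P(A) + P(W) − P(both). In a separate run (4,000 trials, σ 0.8, ρ 0.5) P(A) = 4.4%, P(W) = 4.7% and P(either) = 7.2%, so P(both) = 4.4 + 4.7 − 7.2 = 1.9% and disagreement is 7.2 − 1.9 = 5.3%. Even unrestricted choice between the two p-values therefore adds about 2 points to a nominal 5%.

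*True ratio 0.65.* For the mean there is a closed-form check. The log change has variance 2σ²(1 − ρ), so the unadjusted difference in mean percent change is −35 × exp[σ²(1 − ρ)].

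| σ, ρ | Closed form | Simulated LSM difference | Hodges-Lehmann | Power ANCOVA / Wilcoxon | Disagree |
|---|---|---|---|---|---|
| 0.8, 0.8 | −35 × exp(0.128) = −39.8 | −40.1 | −33.2 | 82.4 / 83.3% | 10.7% |
| 1.0, 0.65 | −35 × exp(0.35) = −49.7 | −50.6 | −31.4 | 37.0 / 42.7% | 20.7% |
| 1.2, 0.5 | −35 × exp(0.72) = −71.9 | −73.2 | −28.1 | 14.9 / 23.1% | 17.8% |

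The largest disagreement was 22.3%, at σ 0.8 and ρ 0.5. The two estimates differ by a factor of 40.1/33.2 = 1.2 to 73.2/28.1 = 2.6. The tests were never both significant in opposite directions.

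**4. Does the evidence favour one method?** No. In the table Wilcoxon gains 0.9 to 8.2 points of power. With mild skew (σ 0.5, ρ 0.5) the order reverses: 87.9% for ANCOVA against 84.0% at ratio 0.65, and 37.5% against 33.4% at ratio 0.80. A log-scale ANCOVA paired with Wilcoxon would also disagree in 8-21% of trials at ratio 0.65. The disagreement is therefore mostly what two different tests produce at modest power, and does not point to a wrong choice.

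**5. Would striking hs-CRP from the ANCOVA list leave one result?** No. SAP 5.3.2 also calls for LOCF and observed-data analyses and repeats the work in the treatment completer set. At Month 2 the mITT set alone gives 2 methods × 2 data rules = 4 p-values; removing a method leaves 2, still unranked.

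**6. What share of the plan is affected?** The secondary efficacy list has 1 + 2 + (4 × 2) = 11 comparisons, each at 0.05 without adjustment. hs-CRP supplies 2 of them and the primary LDL-C test none.

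**The case for a change.** The strongest case for acting is that a label costs one sentence before unblinding and cannot be added credibly afterwards. Having no multiplicity control across endpoints does not license a choice between p-values within one endpoint. The two estimates answer different questions, by a factor of up to 2.6 under the assumptions above, so without a label the planned hs-CRP effect size is undefined. The natural reading also has a weak spot, because 5.3.2 itself names hs-CRP.

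The textual part of this stands: no sentence ranks the two analyses, and a label would be tidier. The consequence is smaller than it looks. Both results are required output, so selective reporting would mean omitting something the SAP says will be provided. The LSM and the Hodges-Lehmann shift are named as such, so a reader can see which is which.

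The case for removing hs-CRP from the ANCOVA list does not stand. Protocol 13.6 and SAP 5.3.2 both name ANCOVA for hs-CRP. Removing it gives up the planned baseline adjustment, and whether power rises or falls depends on a skew the documents do not state.

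**Conclusion.** This is a gap that analysts fill sensibly. Two prespecified analyses of one secondary marker lack a main or sensitivity label. The placement of the Wilcoxon sentence indicates that the rank analysis leads, and both results will be on the page in any case. Each test keeps its size at about 5% or below. Choosing freely between them would raise the null rate to about 7%, in a Phase 2 plan that adjusts none of its efficacy tests. The primary LDL-C analysis and conclusion do not depend on this.

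The disagreement rate of 11-22%, the power comparison and the spread between the two estimates all rest on assumed log-normal hs-CRP, assumed variability and an assumed ratio of 0.65. They show direction, not what this trial will find. The judgement that no change is needed rests on the text: the two instructions are compatible, both are fixed in advance, and removing either brings no clear gain.

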5.3.3 Pharmacokinetics

Plasma concentrations of bemedoic acid and ESP15228 will be expressed in ng/mL. All concentrations below the limit of quantification or missing data will be labeled as such in the concentration data listings. Concentrations below the lower limit of quantification will be treated as zero in summary statistics.

PK observations with missing concentration, missing dose, missing elapsed time will be flagged as such in the concentration data listings and excluded from PK statistical summary.

PK concentration with elapsed time less than 18 or more than 30 hours post-dose (most recent dose) will be flagged as “out of sampling window” in the concentration data listings and excluded from descriptive statistics.

Three trough plasma concentrations of bemedoic acid and ESP15228 will be summarized from patients at pre-dose (T1), T2, and T3 using descriptive statistics, including subject numbers, mean, standard deviation, CV, median and range.

Population PK analysis may be performed if needed. The result will be reported separately from the clinical study report (CSR).

5.4 Safety Endpoints and Analyses

For all safety endpoints, the safety population (SP) will be used. Descriptive summaries will be provided for safety endpoints.

The summarization of AEs will include TEAEs defined as AEs that begin or worsen after the first dose of double-blind study drug administration and ingestion of the first dose of study drug until 30 days after last dose of study drug. The AEs reported during the Repatha run-in period will be summarized separately by overall group. All TEAEs, SAEs, related AEs (to IMP or to Repatha), AEs leading to withdrawal of the study drug or Repatha and study, fatal AEs and AEs of special interest will be summarized by MedDRA System

Organ Class (SOC) and Preferred Term (PT) in descending order of frequency by treatment group.

Clinical safety laboratories, including hematology, blood chemistry, HbA1C, glucose, and urinalysis; PE findings; vital signs; and weight will be summarized by the value and by change from baseline in the value (where appropriate) at each post-baseline time point.

5.4.1 Adverse Events (AEs)

AEs will be coded using the Medical Dictionary for Regulatory Activities (MedDRA) Version 19.1 or later and will be categorized by MedDRA SOC and preferred term (PT). Patients with AEs that are ongoing at study completion or study withdrawal must be followed until resolution, until stable/chronic, or for 30 days after the last study visit, whichever comes first. Summary tables will focus on TEAEs; however, listings will include all AEs (with non-TEAEs flagged).

In summary tables, TEAEs will be counted as “Not Related” if relationship to IMP was assessed as ‘Not Related’ or “Unlikely”. Events will be counted as “Related” if relationship to IMP was assessed as ‘Possible’, ‘Probable’, ‘Definite’, or if relationship to IMP is missing. TEAEs related to the Repatha will be summarized in the similar fashion.

The severity of the AE will be characterized as mild, moderate, or severe, to the following definitions:

- Mild: Events are usually transient and do not interfere with the patient’s daily activities
- Moderate: Events introduce a low level of inconvenience or concern to the patient and may interfere with daily activities
- Severe: Events interrupt the patient’s usual daily activity, are incapacitating with inability to do usual activities, or significantly affect clinical status and warrant intervention and/or close follow-up

The run-un period will be defined as the period subjects receive Repatha prior to Visit T1. It's 3 months prior to Visit T1.

Overviews of TEAEs will be presented by treatment group containing the following counts and percentages for:

- Patients with AE during the run-in period
- patients with TEAEs
- patients with TEAEs by SOC and PT
- patients with AEs during run-in period by SOC and PT
- patients with TEAEs by maximum severity
- patients with treatment-related TEAEs by IMP or by Repatha
- patients with SAE during the run-in period
- patients with treatment-emergent serious adverse events (TE SAEs)
- patients with TE SAEs by SOC and PT
- patients with SAEs during the run-in period by SOC and PT

- patients with TE SAEs by maximum severity
- patients with treatment-related TE SAEs by IMP or by Repatha
- withdrawal from study drug due to TEAEs
- patients with TEAE by PT
- patients with TE SAEs by PT
- patients with study drug-related TEAEs by PT

The AE overview summaries will count a patient at most once in each AE category (at the “highest/most extreme” designation of each category regardless of preferred term) and percentages will be based on the total number of patients in the safety population.

In addition to a comprehensive listing of all AEs (with non-TEAEs flagged), separate listings will be generated for SAEs, AEs resulting in withdrawal of study drug, and AEs with a fatal outcome.

5.4.2 Adverse Events of Special Interest

Across clinical studies to date, the most frequently reported TEAEs associated with the experiences with ETC-1002 included musculoskeletal and connective tissue disorders (pain in extremity, myalgia, arthralgia, and muscle spasms), nervous system disorders (headache), and gastrointestinal disorders (nausea and diarrhea).

As with other lipid lowering medications, adverse events of special interest (AESI) include hepatic disorders (including changes in hepatic aminotransferases), musculoskeletal events (AE and CK evaluation), new onset diabetes/hyperglycemia, renal events, and neurocognitive/neurologic events. These events will be evaluated from the AE database by SOC and PT, and will be identified as safety monitoring endpoints.

- AEs of muscle-related symptoms will be summarized by treatment group. In addition, the number and percent of patients with abnormal CK values will be summarized.
- New onset diabetes/hyperglycemia will be recorded as AEs and will be summarized using the appropriate SOC. The events will be summarized by severity and relationship to study drug for each treatment group.
- Baseline eGFR and values of CK will be summarized by treatment group and by baseline eGFR categories. Shift tables of eGFR category from baseline over the study, will be provided by treatment group.
- Neurocognitive events will be identified and evaluated by routine monitoring of PE findings and AEs. Summarization of neurocognitive events will occur using pre-specified MedDRA terms and will be performed by treatment group.
- Hypoglycemia/Metabolic acidosis occurrences will be summarized based on AE evaluations.

AESI will be presented in a listing and summarized by SOC, PT and treatment group.

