#### **11.1.5.4.3. Monitoring and Management of Elevated Creatine Kinase**

If at any time after randomization a patient experiences a marked CK elevation  $>5 \times \text{ULN}$ , the patient will undergo repeat confirmatory assessment as soon as is reasonably possible, preferably within 3 to 7 days of the laboratory result becoming available.

Repeat CK assessment will include query for related symptoms.

- If the repeat CK assessment confirms an unexplained (ie, not associated with recent trauma or physically strenuous activity) CK abnormality  $>5 \times \text{ULN}$ , if asymptomatic, the patient should receive further assessment and investigation into the cause, assess whether there is renal injury, and measure CK approximately weekly or more frequently if clinically indicated until resolution. If CK levels continue to rise; IMP should be discontinued.
- If symptomatic, the following should be completed:
  - Hold IMP
  - Clarification of the nature, duration, and intensity of muscle symptoms
  - Review possible predisposing factors, such as unaccustomed exercise, heavy alcohol intake, viral illness (consider performing serology)
  - Evaluation for additional diagnoses or other conditions which can cause myopathy including muscle tenderness (by PE), weakness, rash, measurement of serum creatinine, dipstick urinalysis with microscopy if indicated
  - Obtain clinical chemistries to assess the possibility of lactic acidosis
  - Follow symptoms and CK until the abnormality has resolved
  - If based on the above evaluation an alternative explanation is suspected, consideration can be given to resuming IMP once CK returns to baseline levels
  - If no alternative explanation exists, consideration should be given to withdrawing the patient from IMP treatment.
- If the repeat CK assessment confirms an unexplained (ie, not associated with recent trauma or physically strenuous activity) CK abnormality as listed below, the patient should be withdrawn and given no further doses of study drug:
  - $>10 \times \text{ULN}$ , even in the absence of symptoms.
  - In all cases, evaluate the signs/symptoms and laboratory evaluations as outlined above.

- If the patient is withdrawn from IMP treatment, the patient should be asked to continue being followed for safety using the protocol-specified visit schedule (see [Appendix 1](#)).

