#### **11.1.5.5. Monitoring and Management of Potential Hypoglycemia and Metabolic Acidosis**

Patients will be educated on the signs and symptoms of hypoglycemia. If such signs and symptoms are experienced, patients will be instructed to report these signs and symptoms to the investigator.

During each study visit, patients will be reminded to report all signs and symptoms associated with hypoglycemia to the investigator. For each occurrence of patient-reported signs and symptoms associated with hypoglycemia, the investigator will discuss these symptoms with the patient and assess whether they are attributable to hypoglycemia or to another potential cause. All investigator-confirmed occurrences of hypoglycemia will be recorded as an AE. All occurrences of signs and symptoms that are not confirmed by the investigator to be attributable to hypoglycemia will be reported using the appropriate diagnosis.

Clinical laboratories will be assessed to determine any signs of anion gap metabolic acidosis. If laboratories are consistent with metabolic acidosis, immediate follow up with the patient for further medical evaluation of the acidosis will occur. This event should be captured as an AE.

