#### **Hepatic Safety**

For liver-associated enzymes and TB, the number and percent of patients with abnormal values for ALT, AST, and TB will be summarized. All liver-associated laboratory abnormalities will be assessed for Hy's Law criteria ( $\geq 3 \times$  ULN for either ALT or AST, with accompanying TB  $> 2 \times$

ULN in the absence of other known causes) will also be applied to the data; any potential Hy's law cases will be listed separately.

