5.4.3 Laboratory Evaluations

Continuous laboratory parameters (serum chemistry, hematology), urinalysis, urinalysis [microscopic] listed in Table 4; glucose, and HbA1c will be summarized using descriptive statistics for the observed value and the change from baseline for all post-baseline study visits. Missing values for any of the laboratory evaluations will not be imputed; that is, only observed case data will be used. Categorical urinalysis data will be listed, but will not be summarized.

Table 4: Clinical Laboratory Parameters (Safety)

Hematology	Blood Chemistry (serum, fasting)

 • Hematology • Hematocrit (Hct) • Hemoglobin (Hgb) • Mean corpuscular hemoglobin (MCH) • Mean corpuscular hemoglobin concentration (MCHC) • Mean corpuscular volume (MCV) • Platelet count • Red blood (RBC) cell count • White blood (WBC) cell count with differential (absolute and %) 	
 • Albumin (Alb) • Alkaline phosphatase (Alk-P) • Alanine aminotransferase (ALT; SGPT) • Aspartate aminotransferase (AST; SGOT) • Blood urea nitrogen (BUN) • Calcium (Ca) • Carbon dioxide (CO₂) • Chloride (Cl) • Creatinine • Creatine kinase (CK) • Glucose • Lactate dehydrogenase (LDH) • Phosphorus • Potassium (K) • Sodium (Na) • Total and direct bilirubin (TB) • Total protein • Uric acid
Urinalysis (Dipstick)	Coagulation (only in patients receiving anticoagulant therapy that in the investigator's judgment require monitoring at Visit T1 and 3 to 5 days post Visit T1) 
 • Prothrombin time (PT) • International normalized ration (INR)
Urinalysis (Microscopic)-only if urine dipstick abnormal	Additional samples 
 • Hemoglobin A1C (HbA1C) • PK

The number and percentage of patients with laboratory abnormalities (i.e., laboratory values outside the stated laboratory normal range) will be summarized at each time point (i.e., including baseline and post-baseline time points) for each laboratory parameter. The determination of laboratory abnormalities will take into account any unscheduled

laboratory assessments. Additional lab-related summaries will be provided as follows for hepatic safety, musculoskeletal safety, diabetes and hyperglycemia, and renal safety.

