5.4.3.1 Hepatic Safety

For liver-associated enzymes and total bilirubin (TB), the number and percent of patients with abnormal values for ALT ($> 3 \times \text{ULN}$, $> 5 \times \text{ULN}$), AST ($> 3 \times \text{ULN}$, $> 5 \times \text{ULN}$), and TB ($> 2 \times \text{ULN}$) will be summarized by treatment group and overall, normal baseline ALT/AST/TB and abnormal baseline ALT/AST/TB.

Potential Hy's law criteria ($> 3 \times$ upper limit of normal [ULN] for either ALT or AST, with accompanying TB $> 2 \times \text{ULN}$, with no other known cause) will also be applied to the data; any potential Hy's law cases will be listed separately.

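### The SAP's CK count has no severity tier: the announced musculoskeletal laboratory summary is missing, and patients above the protocol's own levels (>5 and >10 × ULN) are not counted

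*SAP*

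**What the plan says.** SAP 5.4.2 lists musculoskeletal events, evaluated through both AEs and CK, among the adverse events of special interest. For CK it plans that "the number and percent of patients with abnormal CK values will be summarized", with no threshold. Protocol 13.7 and the protocol synopsis word the CK count in the same way.

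SAP 5.4.3 explains the general term as "laboratory abnormalities (i.e., laboratory values outside the stated laboratory normal range". It counts such results at each time point and takes unscheduled assessments into account. It then states: "Additional lab-related summaries will be provided as follows for hepatic safety, musculoskeletal safety, diabetes and hyperglycemia, and renal safety". Two subsections follow, 5.4.3.1 (hepatic) and 5.4.3.2 (renal). There is none for musculoskeletal safety or for diabetes and hyperglycemia.

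Protocol 11.1.5.4.3 works with graded CK levels. Repeat testing starts when a "patient experiences a marked CK elevation" above 5 × ULN, and a further level is set at above 10 × ULN. Neither figure appears in the SAP.

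On the liver, Protocol 13.7 says "All liver-associated laboratory abnormalities will be assessed for Hy's Law criteria" and gives the aminotransferase limit as ≥3 × ULN. SAP 5.4.3.1 applies "Potential Hy's law criteria" with a limit of >3 × ULN. Both require total bilirubin >2 × ULN.

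**The concern.** The CK count is the SAP's only patient count based on CK for a named event of special interest. If abnormal means outside the normal range, a result just above ULN and one above 10 × ULN count the same, and nothing in the wording excludes low results. An imbalance between arms in marked elevations could then be hidden among unremarkable results. A reader of the study report could not recover how many patients in each arm reached the levels at which the protocol asks for action.

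The SAP handles the comparable hepatic measure differently: ALT and AST are counted at >3 and >5 × ULN. That contrast, together with the announced block that never appears, suggests an omission rather than a choice.

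**Working it through.** The plan states no figure on this point to reproduce. The check is a comparison of text, followed by an illustration of scale.

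**1. CK criteria side by side**

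- Protocol 11.1.5.4.3 (monitoring): >5 × ULN and >10 × ULN.
- Protocol 13.7 (analysis): abnormal CK, no threshold.
- SAP 5.4.2: abnormal CK, no threshold.
- SAP 5.4.3: an abnormality is any result outside the normal range, counted per time point.
- SAP 5.4.3.1, for contrast: ALT and AST at >3 and >5 × ULN, total bilirubin at >2 × ULN.

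The gap therefore lies between the analysis text of both documents and the protocol's monitoring levels.

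**2. Scale of the pooling (illustration)**

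Inputs from the documents: n = 26 per arm (SAP 4.3) and two scheduled post-baseline visits, T2 and T3 (Appendix 1). Assumptions, not document figures: a chance out-of-range rate p per CK test of 2.5%, 5%, 10% or 20%; independent visits; and a per-patient rate r of CK >5 × ULN of 0.5%, 1%, 2% or 5%.

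- Expected out of range at one visit, 26 × p: 0.65, 1.3, 2.6, 5.2 patients per arm.
- Probability of at least one flag in two visits, q = 1 − (1 − p)²: 0.0494, 0.0975, 0.19, 0.36.
- Expected patients flagged at least once, 26 × q: 1.28, 2.54, 4.94, 9.36.
- Chance of at least one such patient in an arm, 1 − (1 − q)^26: 0.732, 0.931, 0.996, about 1.00.
- Expected patients with CK >5 × ULN, 26 × r: 0.13, 0.26, 0.52, 1.3.
- Chance of at least one, 1 − (1 − r)^26: 0.122, 0.230, 0.409, 0.736.

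In most combinations the out-of-range count is several times the marked count. The ranges meet at one corner (1.28 flagged at p = 2.5%, against 1.3 marked at r = 5%). If results at the two visits were fully correlated, the flagged count would fall to the one-visit figures.

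**3. Hy's law limit**

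- ≥3 × ULN: Hy's law text in the protocol synopsis and in Protocol 13.7. The synopsis trigger for hepatic investigation is also at 3 × ULN or more.
- >3 × ULN: Protocol 11.1.5.4.1, Protocol 12.3 and SAP 5.4.3.1.

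The two forms differ only at exactly 3 × ULN. For enzymes reported as whole numbers, with assumed ULNs of 30, 35, 40, 45 and 55 U/L, one result per ULN is affected: 90, 105, 120, 135 and 165 U/L. SAP section 6 does not list this difference among its changes.

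**The case against.** The best defence on CK is that other planned outputs would reveal a problem. CK is summarized by visit with change from baseline, the general rules in SAP 5.1 include the maximum, and CK is also summarized by baseline eGFR category. This largely stands: it would be wrong to infer that a marked elevation must go unseen. But a maximum does not say how many patients crossed a level. The SAP brings unscheduled assessments into the abnormality counts, but does not say whether a peak at an unscheduled repeat enters the by-visit statistics.

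A second defence is that applying the definition in 5.4.3 to the word in 5.4.2 is an inference, since 5.4.3.1 uses the same adjective for multiples of ULN. That is fair. On that reading the CK criterion is undefined rather than badly defined, and the remedy is the same.

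Four stronger readings are tempting, and the documents do not support them.

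- *The SAP ignores the protocol's laboratory criteria in general.* Its ALT, AST and total bilirubin levels match those in Protocol 11.1.5.4.1.
- *The CK wording is an undeclared departure from the protocol.* It repeats Protocol 13.7, so SAP section 6 had no change to list.
- *Laboratory acidosis is lost because* "Hypoglycemia/Metabolic acidosis occurrences will be summarized based on AE evaluations". Protocol 11.1.5.5 does say "Clinical laboratories will be assessed to determine any signs of anion gap metabolic acidosis", but it sets no numeric criterion and directs that acidosis found in this way be recorded as an AE. The SAP also summarizes sodium, chloride, carbon dioxide and glucose individually. An anion-gap summary would be an optional extra.
- *Patients with Gilbert's disease are miscounted because the SAP uses total bilirubin.* The direct-bilirubin note in Protocol 11.1.5.4.1 belongs to a rule on stopping study drug. The protocol's own analysis definition in 13.7 uses total bilirubin.

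**Conclusion.** The CK point holds. The prespecified CK count for a named event of special interest has no severity tier, the announced musculoskeletal block is absent, and the number of patients per arm above 5 and 10 × ULN is not among the planned outputs. That is a gap in a descriptive safety summary. All safety analyses here are descriptive, so neither alpha nor power is affected.

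The size can only be illustrated: roughly 1.3 to 9.4 patients per arm flagged by chance, against 0.13 to 1.3 with CK >5 × ULN. Both ranges depend on assumed rates, and the first also on independent visits. The tiered count will not make 26 patients per arm informative about rare events: even 0 of 26 leaves an exact two-sided 95% upper limit of 1 − 0.025^(1/26) = 13.2%. Its value is that it reports the relevant count.

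The Hy's law difference is real but minor. It touches only results at exactly 3 × ULN, and the protocol is inconsistent within itself, so it should not be read simply as the SAP shifting a settled protocol limit.

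**What to change.** In SAP 5.4.3, add the announced musculoskeletal subsection: number and percent of patients, by treatment group, whose worst post-baseline CK is >5 × ULN and >10 × ULN, including unscheduled assessments. These are the levels already in Protocol 11.1.5.4.3, and the change is to reporting only. In 5.4.2, state what abnormal CK means or refer to the new subsection. Either supply the announced diabetes and hyperglycemia block or remove the announcement.

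Reconcile the Hy's law aminotransferase limit across the protocol synopsis, Protocol 11.1.5.4.1, 12.3 and 13.7, and SAP 5.4.3.1, so that one limit is used. If a difference from the protocol remains, list it in SAP section 6.

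The cost is SAP wording and one extra descriptive CK table from data already collected. No new visit, sample or procedure is needed.
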